# 14.1.2. Process evaluation(qualitative element)

We will select eight intervention and eight control stores from which consumers and retail sector personnel recruited to take part in the qualitative element of the process evaluation will be selected. One focus group discussion with customers will be conducted per store, and two for any store with a particularly heterogeneous customer base, giving a total of around 18 focus groups. We will conduct individual interviews with two retail sector personnel per selected store – 32 interviews in total. We envisage 5-10 individual interviews with intervention implementation professionals.

#### 15. ANTICIPATED START DATE

01/08/2010

# **16. ANTICIPATED END DATE**

31/01/2013

#### 17. DISEASE, CONDITION OR STUDY DOMAIN

Public health nutrition, public health policy, food retailing, diet. In particular, the effect of a specific policy led food retailing intervention on fresh fruit and vegetable intake.

#### 18. INTERVENTIONS

#### 18.1. Intervention arm

The c-store C4L FFV intervention implemented in development stores involves an in-store 'toolkit', an in-store Fresh Food Champion, and regular support from the DH implementation team. As retailers make a substantial financial contribution to the cost of the intervention, it also involves the presence of a committed retailer. Although the main intervention components are consistent across stores, there will naturally be store-to-store variation in implementation, as expected in a pragmatic trial.

# 18.1.1. In-store toolkit

The in-store toolkit comprises C4L branded chiller cabinet, impulse stand, ambient shelving, on-street A-stand, and vinyl window display. The total cost of this is in the region of £15-20,000 per store depending on size and any alterations required to accommodate the new materials. DH contributes an average of £3000 per store, and retailers make up the difference.

# 18.1.2. Fresh Food Champion

The in-store Fresh Food Champion is a member of staff who takes responsibility for the C4L branded units and product lines sold from them. This is the main point of contact between the DH implementation team and individual stores. The champion receives a DVD tutorial, and is responsible for ensuring that all branded units are used as intended and that the freshness of produce is maintained.

# 18.1.3. Support from the regional managers and DH implementation team

Symbol groups maintain contact with individual stores through regional managers. This network of individuals visit stores around fortnightly in order to maintain the branding of the group, pick up store managers' orders, and provide an informal support mechanism. This established network will be used by the DH implementation team as liaison workers. In addition to their ongoing duties, regional managers will provide information on use of the C4L toolkit, help retailers manage bulk purchasing and in-store product placement, and provide on-going informal support. This additional role for regional managers is facilitated by the presence of key decision makers from each of the symbol groups involved in the programme on the C4L c-store FFV intervention steering group.

#### 18.2. Control arm

The control condition will be usual practice. Stores will be free to make any changes to layout and inventory they wish. Control stores will not have access to financial support from DH, or specific C4L related support from the DH intervention team, or symbol group regional managers during the 12 months of the intervention period. The intervention will be made available to control stores, should they wish it, following final data collection.

#### 18.3. Duration of treatment

The in-store toolkit will not be withdrawn once it is in place in study stores—although it is possible that DH may provide updated in-store materials in the future. As DH has earmarked funding for the intervention until 2011, we envisage that support from the DH implementation team will last at least until 2011. Use of the in-store toolkit and in-store Fresh Food Champion is likely to vary from store-to-store, and with time.

# 18.4. Duration of follow up

#### 18.4.1. Cluster RCT

Data will be collected from individual cluster RCT participants at baseline and 12 month follow up.

#### 18.4.2. Process evaluation

Quantitative process evaluation data will be collected from study stores at baseline immediately before intervention implementation, and 1 and 12 months after intervention implementation. Qualitative process evaluation data will be collected around 8 months after intervention implementation.

# 19. PRIMARY OUTCOME MEASURE(S)

The primary outcome (change in FFV consumption) amongst individual cluster RCT participants will be measured as change in mean grams of FFV consumed per day using two-day food diaries, based on the methods used in the National Diet and Nutrition Survey (NDNS). Diet will be recorded over two consecutive days, with study days at baseline and follow up varying between, but not within, participants. Approximately equal numbers of individuals per store will begin recording their diet on each day of the week.

#### 20. SECONDARY OUTCOME MEASURE(S)

Secondary outcomes will be measured at the individual level in the cluster RCT. Additional store level measures will be used in the economic evaluation and in the quantitative element of the process evaluation.

#### 20.1. Cluster RCT

The secondary outcome measured in cluster RCT participants will be change in other markers of dietary quality – in particular, percent of dietary energy derived from fat, for which there is a clearly defined UK recommendation,(18) and energy density of food intake, which would be expected to reduce with increased consumption of low energy dense foods such as FFV.(19) These will also be derived from two-day food diary data as per primary outcome measurement.

#### 20.2. Economic evaluation

The customer centred outcome measures to be used in the economic evaluation will be the same as those in the cluster RCT. We will seek to gauge the impact of the intervention on stores' revenues using electronic point of sales (EPOS) data. Data will be collected at 12 months from the intervention stores and regional managers and DH on the specific costs of intervention implementation. Estimates of costs to consumers of any changes in diet will be made using food diary data and contemporary price data for specific foods and

food categories. We will then derive summary measures of costs associated with the intervention as they fall on DH, on stores and on individual consumers.

#### 20.3. Process evaluation

The quantitative element of the process evaluation will allow consideration of a number of markers of process at the store and individual level.

#### 20.3.1. Stores

At the store level, the primary quantitative marker of process will be change in sales of FFV measured as total turnover from FFV per week using EPOS data provided by store managers over one week at baseline, one month and 12 month follow up. These data are collected by electronic bar-code scanners already installed in stores. Secondary markers of process measured using EPOS data will be change in range of FFV sold, change in proportion of total sales accounted for by FFV, and change in proportion of baskets that include FFV. Secondary markers of process, measured from data collected during in-store observations at baseline, one month and 12 month follow up, will be change in:

- variety of FFV available, measured as the number of different FFV lines on sale
- cost of FFV, measured as the proportion of FFV lines on sale at below the median price for that line across all stores in the study
- quality of FFV, measured as proportion of FFV lines on sale judged by appearance to be of good quality

In intervention stores we will also assess fidelity and standard of the implementation of the intervention at baseline, one month and 12 month follow up, using in-store observations and a data collection instrument covering key aspects of intervention implementation derived from the guidance and documentation provided to store managers with C4L materials. We will also take digital photographs of the inside and outside of study stores to keep a permanent visual record of the use of C4L branded materials and FFV displays.

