#### 8. STUDY OBJECTIVES

The primary objective is to answer the question: does the C4L c-store FFV intervention lead to a statistically significant increase in consumption of FFV over 12 months among regular users of intervention stores, compared to regular users of control stores?

Secondary objectives will be to answer the questions:

- What is the effect of the intervention at 12 months on change in other markers of dietary quality among regular users of intervention stores, compared to regular users of control stores?
- What are the resource consequences of the intervention at 12 months and how do they relate to intervention outcomes?
- What is the effect of the intervention on change in shopping habits at 12 months among regular users of intervention stores, compared to regular users of control stores?
- What is the effect of the intervention at 1 and 12 months on change in sales variety, cost and quality of FFV in intervention stores, compared to control stores?
- What variation is there in implementation of the intervention at 1 and 12 months?
- What is the feasibility, acceptability and unexpected consequences of the intervention at 8-10 months among key stakeholders including consumers, retail sector personnel (store managers and owners, instore Fresh Food Champions (see section 18.1.2), and other staff) and intervention implementation professionals (decision makers from the Department of Health, the Association of Convenience Stores and the symbol groups involved in the intervention)?

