We calculate that a total achieved sample size at follow up of 692 individual participants and 28 c-stores (14 intervention and 14 control) is required to detect as statistically significant a mean difference in the change in FFV intake between study groups of 40g (standard deviation of the differences 2.1 portions, 80% power, 5% significance level, two-sided test, ICC 0.01). This equates to 25 individual participants per store. Assuming 35% attrition between baseline and follow up,(15) the total number of individual participants recruited at baseline per c-store increases to 38 and the total sample size at baseline to 1064. Assuming a recruitment rate of 40%, (similar to that in previous work; [name], personal communication), the total number of individuals that we will invite to take part will be approximately 2660.

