# 21.1.1. Sampling of stores

A sampling frame of all stores meeting the inclusion criteria, except the distance criterion (see section 11.1.1), will be supplied by relevant individuals at DH & ACS. All stores in the sampling frame will be stratified according to Government Office Region, socio-economic deprivation and store size. The exact nature of the deprivation and size strata will be determined once data on these stratifying variables have been examined. Pairs of stores (which are more than 1km from each other or other pairs) will then be randomly selected from each stratum for inclusion in the research. If stores are selected that are within 1km of previously selected stores, re-sampling will take place. Within each pair one store will be randomised to the intervention arm of the study and one to the control arm.

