#### 23.3. Process evaluation

#### 23.3.1. Quantitative element

Collection of shopping habits data is detailed in sections 23.1.1 and 23.1.2. The other aspects of the quantitative process evaluation are analyses of EPOS data and in-store observations. Information on sales of FFV over one week at baseline, one month and 12 month follow up will be provided by store managers from their EPOS records.

Information on available FFV will be assessed by direct observation by researchers visiting individual stores. An in-store observation instrument will be used to collect data at baseline; one and 12 month follow up to assess variety, cost and quality of FFV and to assess how the intervention has been implemented in intervention stores at one and 12 month follow up. With store managers' permission, we will also take digital photographs of the inside and outside of study stores to keep a permanent record of use of C4L branded materials and FFV displays. Cost comparison data will be accessed via web based searches of a major high street retailer's on-line store for the costs of a comparable range of FFV to that currently available in the study c-store within eight days of each individual c-store visit.

Although researchers will make themselves known to managers on arrival for observations and seek permission to conduct observations, these visits will be unannounced.

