#### 37. FLOW DIAGRAM SHOWING ALL STUDY COMPONENTS

# 38. TIMELINE

Activity 1	re	Staff cruitme	ent		nics roval			indivi	ect & re iduals, ntrol ste	3 inter	ventio	n & 3	ch	seline o ecking ning, cl RCT	&					coll indiv	ection iduals,	n follov from cl 3 inter ores p	uster F ventio	RCT n & 3	ch	onth for up data ecking ning, cl RCT	a   &		a analy			Data pretation portin	
Activity 2	(	Externa contrac nalisati	t			Sel- reco rando sto	ruit, omise	Baseline data collection from cluster RCT individuals, 3 intervention & 3 control stores per month*			Pilot focus groups and individual in- depth interviews				Select & recruit qualitative process evaluation participants, 1 intervention & 1 control store per month						Transcription & analysis of focus group and individuals interview data					Data analysis , quantitative process evaluation							
Activity 3				confi m	rm acc ethods	roups feeptabiles; finalisment to	ity of se	In-store baseline data collection, 3 intervention & 3 control stores per month*							Focus group and individuals in- depth interviews, 1 intervention & 1 control store per month				Implement intervention, control stores, 3 stores per month*						Data analysis, economic evaluation								
Activity 4						amplin strateg	_	Implement intervention intervention stores, 3 sto per month*						data colle			collect	2 month follow up ction, 3 intervention I stores per month*															
Activity 5									In-store 1 month data collection, 2 ir & 2 control stores p		! intervention																						
Milestone			1		2		3, 4					5, 6	7	8								9		10		11				12			13
Month	-3	-2	-1	1	2	3	4	5	6	7	8	9	10	11	12	13	14	15	16	17	18	19	20	21	22	23	24	25	26	27	28	29	30
	May 10	June 10	July 10	August 10	September 10	October 10	November 10	December 10	January 11	February 11	March 11	April 11	May 11	June 11	11 yluC	August 11	September 11	October 11	November 11	December 11	January 12	February 12	March 12	April 12	May 12	June 12	July 12	August 12	September 12	October 12	November 12	December 12	January 13

\*3 stores per month for first four months and 2 stores in the final month

All elements Cluster RCT Process evaluation Economic evaluation Intervention implementation Milestones
--

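### The EPOS sales markers use one unspecified, unmatched week per time point, which costs avoidable precision in a 14 v 14 store comparison.

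*Protocol*

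**What the plan says.** Protocol section 20.3.1 states: "At the store level, the primary quantitative marker of process will be change in sales of FFV". It is expressed as total FFV turnover per week and obtained "using EPOS data provided by store managers over one week at baseline, one month and 12 month follow up". The range of FFV sold, the FFV share of total sales and the proportion of baskets containing FFV also come from EPOS data. On the source, the section says: "These data are collected by electronic bar-code scanners already installed in stores". Section 23.3.1 repeats the window: "Information on sales of FFV over one week at baseline, one month and 12 month follow up will be provided by store managers". The marker serves a named secondary objective in section 8: "What is the effect of the intervention at 1 and 12 months on change in sales variety, cost and quality of FFV".

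Four other parts of the protocol bear on the point:

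- **Pairing.** Section 21.1.1 samples stores in stratified pairs: "Within each pair one store will be randomised to the intervention arm of the study and one to the control arm".
- **Monthly quota.** The timeline in section 38 has the entry "In-store baseline data collection, 3 intervention & 3 control stores per month", with three stores per arm in each of the first four months and two in the last.
- **Dates.** The milestones in section 39 end baseline collection in April 2011, one-month collection in June 2011 and 12-month collection in April 2012.
- **Status.** Section 28.1.2 confines formal hypothesis testing to the individual-level primary outcome.

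The protocol does not say which week is extracted, whether the two stores of a pair share it, or how holiday weeks are treated.

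**The concern.** Weekly sales in a small shop vary with holidays, promotions and deliveries. A change score built from two single weeks carries that variation twice, and with 14 stores per arm little averaging remains. The scanners already record these data, so restricting the extract to one week gives up precision that would be cheap to have.

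The calendar adds to the noise. Counting five months back from the April 2011 milestone puts baseline at about December 2010 to April 2011. Christmas and Easter can therefore fall in some stores' weeks and not in others'. At 1 month, baseline and follow-up will usually lie in different calendar months, so seasonal change sits inside each store's change score.

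What is at stake is how well the study can say whether FFV sales changed, which is a link between the intervention and any change in diet. This is more than detail left to an analysis plan: the protocol itself sets the window at one week, and weeks that are not requested cannot be analysed.

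**Working it through.** **The plan's own figures.** The protocol gives no variance, sample size or power for the EPOS marker, so there is no stated figure to reproduce for it. The 692 in section 14.1.1 belongs to the individual-level outcome and does reproduce: 277 per arm (difference 0.5 portions, SD 2.1, 80% power, two-sided 5%) × 2 × a design effect of 1.25 = 692.5. With a design effect of 1 + 24 × 0.01 = 1.24 the result is 687.

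**Precision of the arm difference.** Let sb be the between-store SD of true log change, sw the week-to-week SD of log turnover, and k the number of weeks per time point. For an unpaired comparison of 14 v 14 stores with independent weeks:

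SE = √[(2/14) × (sb² + 2·sw²/k)]

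The factor 2 on sw² is the noise counted once at baseline and once at follow-up. All SDs are assumptions.

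| sb | sw | SE, k = 1 | SE, k = 4 | Reduction |
|---|---|---|---|---|
| 0.2 | 0.3 | √(0.22/7) = 0.177 | √(0.085/7) = 0.110 | 38% |
| 0.2 | 0.2 | √(0.12/7) = 0.131 | √(0.06/7) = 0.093 | 29% |
| 0.3 | 0.2 | √(0.17/7) = 0.156 | √(0.11/7) = 0.125 | 20% |
| 0.4 | 0.2 | √(0.24/7) = 0.185 | √(0.18/7) = 0.160 | 13% |

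If weeks within a window have correlation r, then sw²/4 becomes sw²(1 + 3r)/4. The gain shrinks as r rises and vanishes at r = 1.

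**As a detectable difference.** This is the difference between arms in change, as a share of baseline sales, at 80% power, two-sided 5% and 26 df. The assumed weekly CV is 0.20 and tau is the between-store SD of true change.

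- tau = 0: 31% with one week, 16% with four.
- tau = 0.2: 38% with one week, 27% with four.
- tau = 0.4: 54% with one week, 47% with four.

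The benefit is large only where week-to-week noise is the main source of variation.

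**Calendar.** By quota, 6 of 28 stores (21%) have baseline in the first month, about December, and 4 of 28 (14%) in the last, about April. Easter falls on 24 April 2011 and 8 April 2012, so the same calendar week a year apart need not match for April stores. Each arm has 3/14 of its stores in the first month, so a shared seasonal shift contributes 3/14 − 3/14 = 0 to the expected arm difference. Balance by month is not balance by week: two stores of a pair measured in the same month can still supply different weeks.

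**Influence of one odd week.** A store has weight 1/14 in its arm mean. A week that is off by 50%, 100% or 200% of baseline sales moves that mean by 3.6, 7.1 or 14.3 points. At weekly CV 0.20 and tau = 0 the SE of the arm difference is √2 × 0.20 × √(2/14) = 0.107, or 10.7 points, so these shifts are 0.33, 0.67 and 1.34 SE. In a simulation with one such store and no true effect, a two-sided 5% t-test rejected in 4.9%, 4.7% and 2.5% of runs.

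**The case against.** The case against acting is substantial. The design already protects the comparison: arms are balanced by month, pairs are split between arms, and the milestones place the 12-month round in about the same calendar months as baseline. Holidays therefore mostly add scatter. The marker is a process measure, tested informally, and neither the primary outcome nor its sample size depends on it. The gain rests on assumed variances, and consecutive weeks are unlikely to be independent. FFV share of sales and share of baskets are ratios, so a busy week partly cancels in them. Longer extracts also enlarge the transaction data needed for the basket analysis in section 28.3.1.

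Most of this stands, and it limits the point to precision. It does not remove it. Monthly balance does not match weeks within a pair, and it does not bring baseline and 1-month follow-up into the same season. The 12-month match is not fully secure either: section 18.4.2 counts from implementation, which section 39 completes at the end of May 2011, while 12-month collection ends in April 2012.

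A reader might infer three stronger things that the protocol does not support:

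- **That one atypical week could dominate the comparison.** A weight of 1/14 rules this out for all but an extreme week. Turnover in absolute pounds would give a large store more weight, but no store sales are given to test that.
- **That a positive result could reflect one holiday week.** The simulated false-positive rate did not rise.
- **That participant sampling is distorted.** Section 21.1.3 estimates footfall from baseline EPOS data but does not say it uses the same one-week extract.

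**Conclusion.** The point holds as a minor, cheap improvement in precision. One unspecified and unmatched week per time point makes the sales markers less precise than the available records allow, most clearly at 1 month. Going from one week to four lowers the SE of the arm difference by about 13% to 38%. That range assumes between-store SDs of 0.2 to 0.4, weekly SDs of 0.2 to 0.3 (log scale), an unpaired 14 v 14 comparison and independent weeks; correlated weeks give less. The calculation is for turnover, and the ratio markers may gain less. It shows no bias between arms and no inflated error rate, and it leaves the trial's primary outcome untouched.

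**What to change.** In sections 20.3.1 and 23.3.1, replace the single week with several weeks of EPOS data at each time point, for example four consecutive weeks, and analyse mean weekly values. State the window rule:

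- The baseline window ends before any fit-out.
- Both stores of a pair use the same calendar weeks at every time point.
- The 12-month weeks are aligned with the baseline weeks relative to Christmas and Easter.

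Reconcile section 18.4.2 with the milestones, so that it is clear what the 12 months are counted from.

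The number of data requests stays at three. The cost is larger extracts to supply and clean, including for the basket analysis, and some stores may return fewer weeks, in which case the available weeks can be averaged. The protocol does not say how long stores keep transaction records, so this should be checked before baseline. If only one week is feasible, stating and matching the week is still worth doing.

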#### 24. BLINDING

Blinding will only be of importance in the cluster RCT – participants in the qualitative element of the process evaluation will be actively encouraged to discuss the intervention. At baseline, we will not inform fieldworkers or individual cluster RCT participants what the intervention being studied is, nor whether stores have been allocated to the intervention or control group. By 12 month follow up it is possible that both individual cluster RCT participants and fieldworkers will have noticed local C4L branded c-stores. However, again we will not specifically tell either participants or fieldworkers what the intervention being studied is. There will be some questions concerning awareness of the intervention at follow up so. For these reasons, we will not be able to prevent awareness of the intervention or group allocation by 12 month follow up in all cases and the cluster RCT technically falls within the definition of an 'unblinded' RCT.

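### Fruit and vegetable quality is rated by eye, by observers who will know the arm at follow-up; any arm-related rating shift stays in the between-arm comparison of change, and section 24 overlooks this

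*Protocol*

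**What the plan says.** - **Objective.** Protocol section 8 lists among the secondary questions the effect, at 1 and 12 months, on "change in sales variety, cost and quality of FFV in intervention stores, compared to control stores".
- **Measure.** Section 20.3.1 gives three in-store observation markers. Variety is a count of lines, and cost is a share of lines below a median price. The third is "quality of FFV, measured as proportion of FFV lines on sale judged by appearance to be of good quality".
- **Raters.** Section 23.3.1: "Information on available FFV will be assessed by direct observation by researchers visiting individual stores". The same instrument is used to "assess variety, cost and quality of FFV and to assess how the intervention has been implemented in intervention stores". Researchers also photograph the use of branded materials.
- **Visible sign of the arm.** Section 18.1.1: "The in-store toolkit comprises C4L branded chiller cabinet, impulse stand, ambient shelving, on-street A-stand, and vinyl window display". Section 18.4.2 puts the baseline store visit just before implementation and the later visits 1 and 12 months after it. Control stores follow usual practice (section 18.2).
- **Masking.** Section 24 opens with "Blinding will only be of importance in the cluster RCT". Among research staff, section 24.1.3 covers only the contracted fieldworkers who visit individuals. In-store observers are not mentioned.
- **Timing of the fidelity check.** Section 20.3.1 places it at baseline, one month and 12 months. Section 23.3.1 has the instrument used "to assess how the intervention has been implemented in intervention stores at one and 12 month follow up", with no baseline assessment.

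**The concern.** Of the three in-store markers, quality is the one that depends on the rater's opinion, and it is compared between arms. An observer who completes the implementation part of the form, in a store with a branded chiller and window display, cannot be unaware of the arm. Section 18.1.2 makes freshness of produce part of the in-store champion's job, so the observer also has a reason to expect better produce there.

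Analysing change from baseline looks like protection, but it removes only what is constant over time within a store or common to both arms. A shift that appears with the branding is neither. At stake is the reading of one process marker: an apparent gain in quality could partly reflect the rater, and an adverse shift could hide a real gain. Section 7.1 names poor availability and quality as a long-standing reputation of the sector, so readers are likely to take an interest in this marker.

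**Working it through.** **No planned figure to reproduce.** The protocol gives no SD, target difference, rater agreement or power for quality. The only design figure used is the 14 intervention and 14 control stores of section 14.1.1.

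**Step 1: what taking change removes.** Let b be the mean rating error (as a proportion of lines), with I and C for the arms and 0 and 1 for baseline and follow-up. The bias in the between-arm contrast of change is

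(bI1 − bI0) − (bC1 − bC0).

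| Assumed pattern | bI0 | bI1 | bC0 | bC1 | Bias |
|---|---|---|---|---|---|
| Shift only in intervention stores after baseline | 0 | 0.10 | 0 | 0 | 0.10 |
| As above, and control stores marked down | 0 | 0.10 | 0 | −0.05 | 0.15 |
| Half already present at baseline | 0.05 | 0.10 | 0 | 0 | 0.05 |
| Fully present at baseline | 0.10 | 0.10 | 0 | 0 | 0 |
| Same shift in both arms after baseline | 0 | 0.10 | 0 | 0.10 | 0 |

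The bias is zero when the error changes equally in the two arms, and otherwise it remains. The protocol does not say which pattern applies. Branding that is absent at baseline and present later in one arm makes the first three rows plausible. A fidelity check at baseline, as in section 20.3.1, would move towards the third or fourth.

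**Step 2: how large it might be.** All inputs here are assumptions. If 20% of lines are borderline and half of them are upgraded in branded stores, the shift is 0.20 × 0.5 = 0.10. If a quarter are upgraded, it is 0.20 × 0.25 = 0.05.

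**Step 3: chance of a nominal two-sided p < 0.05 with no true effect.** Two-sample t-test on store-level change, 14 v 14, df = 26, noncentrality = bias / (SD × √(2/14)). For bias 0.10 and SD 0.10 this is 0.10 / (0.10 × 0.378) = 2.65.

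| SD of store-level change (assumed) | Bias 0 | Bias 0.05 | Bias 0.10 |
|---|---|---|---|
| 0.10 | 5% | 25% | 72% |
| 0.15 | 5% | 14% | 40% |
| 0.20 | 5% | 10% | 25% |
| 0.25 | 5% | 8% | 18% |

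This test ignores the pairing of stores (sections 21.1.1 and 22), for which the protocol gives no within-pair correlation for quality.

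**The case against.** - **The rating form is not shown.** Section 40.1 lists an in-store observation checklist (A23). It may contain rating criteria, so the one-line definition does not prove that the judgement is unstructured. This stands, and the fix is conditional on it. Criteria would reduce the subjectivity but would not mask the rater.
- **Section 24 is aimed at something else.** The sentence goes on to contrast the trial with the qualitative element, where participants are meant to discuss the intervention, and the study is already declared unblinded. This largely stands: the sentence reads as an oversight about the in-store ratings, not a considered claim about them. As written, though, it still excludes a between-arm comparison that uses a subjective rating.
- **The marker carries limited weight.** Section 28.1.2 reserves formal testing for the primary outcome, the leading store-level marker is sales turnover, and section 28.4 does not name quality ratings among its store-level sources. This stands and limits the severity.
- **One-arm, follow-up-only bias.** A reader might infer that the bias arises only in intervention stores, only after baseline, and is kept in full. The documents do not establish that: observers can also recognise control stores by the missing branding, and section 20.3.1 places a fidelity check at baseline.
- **Visit timing.** A reader might also take unmatched weekday and time of visit as a source of bias. Nothing in the protocol makes timing differ by arm, so on this text it adds noise only.

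**Conclusion.** The point holds in a limited form. A quality rating made by eye, by observers who will know the arm at 1 and 12 months, is compared between arms, and the section on blinding does not recognise it. A rating shift that differs by arm after baseline passes into the contrast in change.

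The size and direction of any shift are unknown. The 5- and 10-point shifts, the share of borderline lines and the SDs are all assumed, and the probabilities from 8% to 72% mostly reflect those choices. A reader might infer from the upper figure that a false quality effect is likely, or that the evaluation would credit the intervention with a mechanism it lacks. The documents support neither: they give no rater data, and tests of this marker are informal.

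The primary outcome is not affected. This is a modest improvement worth making before baseline store visits begin.

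**What to change.** 1. **Section 20.3.1.** Unless checklist A23 already does this, define good quality as the absence of pre-specified yes/no visible defects (for example mould, wilting, bruising or split skin), applied in the same way to every fruit and vegetable line on sale in all stores. Score it before the implementation section at each visit. A fixed list of common items may be added as a sensitivity measure. It should not replace the stated measure, because it would drop lines outside the list, including any that the intervention adds.
2. **Section 24.** State that in-store quality ratings are unmasked and will be interpreted accordingly.
3. **Sections 20.3.1 and 23.3.1.** Reconcile them on whether fidelity is assessed at baseline, since this bears on what observers know when they make the baseline rating.
4. **Optional.** Visit the two stores of a pair on a similar weekday and in a similar time band. This is a gain in precision, not a correction for bias.

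**Cost.** A revised form before baseline visits and a slightly longer checklist, with no extra staff. The optional matching would reduce freedom in scheduling visits.

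**What remains.** The rater still sees the branding on arrival, and defects such as wilting keep an element of judgement, so the change reduces the bias without removing it.
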